## 4.2. Schedule of Assessments

The schedule of assessments is presented in [Table 1](#). Assessment time points include an enrollment visit, a baseline visit, and follow-up visits at Months 1, 3, 4, 6, 9 and 12. An additional safety assessment will be performed remotely 4 months after the last study treatment dose. Subjects who discontinue treatment early will still be evaluated during the safety follow-up visit (i.e., 4 months after treatment and study discontinuation). Subjects having tentative disability progression identified near the end of the core study (e.g., Month 12) will attend additional follow-up visits 12 and 24 weeks later to confirm progression.

Magnetic resonance imaging (MRI) scans will be performed at the enrollment visit (no later than 7 days prior to the first dose of daclizumab), and at Months 1, 4, 6 and 12. MRI scans will be performed under the supervision of a trained radiologist. Ad-hoc MRI scans may be performed as needed, such as in the event of a MS relapse, in order to rule out a progressive multifocal leukoencephalopathy (PML) diagnosis.

Blood chemistry and hematology assessments will be performed at baseline and at Months 1, 3, 6, 9 and 12. Hematology assessments will include a complete blood count (CBC). Liver function tests (LFT) [alanine transaminase (ALT)/ aspartate transaminase (AST)] will be done at enrollment and monthly visits. Bilirubin testing must be done together with the first AST/ALT test at the enrollment visit. Bilirubin testing must also be done if ALT/SGPT (serum glutamic pyruvate transaminase), or AST/SGOT (serum glutamic oxaloacetic transaminase)  $>3*$ upper limit of normal (ULN), since treatment must be permanently discontinued with the concomitant elevation of total bilirubin  $>2*ULN$ .

At the end of the study, liver monitoring will be done per routine clinical practice.

A safety follow-up visit at 4 months after the last dose of daclizumab provided by the study will be conducted remotely to evaluate potential delayed safety outcomes. The assessments during the additional safety follow-up period will include all safety endpoints described in [Table 1](#). Liver function tests (LFT) will be performed only if the subject is continuing daclizumab or if the subject is within 4 months since study treatment discontinuation, and monitoring is deemed appropriate by the Investigator.

CONFIDENTIAL

The information contained herein may not be used, disclosed, or published without the written consent of  

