## Efficacy and Safety of Daclizumab in Subjects with RRMS Switching from Natalizumab

1. Written informed consent must be obtained prior to start of the study.
2. Screening MRI should occur no later than 7 days prior to the first dose of daclizumab. For subsequent visits, MRI scan can be performed up to 4 days prior to the visit. Ad-hoc MRIs may be conducted as needed, such as in the event of a relapse to rule out PML diagnosis.
3. This is required only for females of child-bearing potential. A urine pregnancy test will be performed monthly.
4. Liver function tests (LFTs) are required to be performed monthly (either on-site or via home visits at Month 7, 8, 10 and 11, if applicable), and samples will be analyzed centrally for the purposes of this study. Results from either local or central LFT tests can be used for medical management of the patient and to determine whether dosing should continue or be suspended at the monthly dosing timepoint. In cases where local LFTs were performed, samples must also be collected for central analysis.
5. Liver function tests (LFTs) during the safety follow-up will be performed only if the subject is continuing daclizumab or if the subject is within 4 months since study treatment discontinuation, and monitoring is deemed appropriate by the Investigator; Abnormal AST/ALT values as described in the product label will lead to treatment suspension or discontinuation.
6. [REDACTED]
7. Samples will be analyzed centrally.
8. Daclizumab dosing will start at baseline and occur monthly until Month 11. Doses at baseline and Months 1, 2, 3, 4, 5, 6 and 9 will be administered in the clinic, and doses at Months 7, 8, 10 and 11 can be administered at home or in the clinic. Daclizumab dosing will not begin until a minimum of 28 days have passed since last natalizumab dose. Before a monthly dose of daclizumab is given, LFT results from a prior test performed within the previous 28 (+3) days must be reviewed by the Study Neurologist or their backup.
9. Subjects will be provided a dosing diary at the Month 6 and Month 9 visits to record observations for home dosing only; home dosing is possible for Month 7, 8, 10, and 11. A window of  $\pm 4$  days applies to daclizumab dose even if it is done at home; subjects should be appropriately instructed on daclizumab self-administration using the autoinjector.

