### **10.1. Dosing Regimen and Administration**

Refer to and follow the prevailing local labeling, directions for handling and administration (DHA) and Investigator Brochure.

Daclizumab is supplied as a sterile, preservative-free, colorless to slightly yellow, and clear to slightly opalescent liquid. The drug product is supplied in a single-use pre-filled pen, also known as an autoinjector, in this study. Daclizumab is supplied as 150 mg of daclizumab per 1.0 mL and is administered SC once a month.

As shown in the study schematic, doses at Months 7, 8, 10 and 11 can be administered either at home or supervised at the site. Therefore, at Months 6 and 9, subjects choosing to self-administer at home will be provided with 2 kits to take home along with cool bags and sharp bins.

Subjects should be trained in the proper technique and storage for self-administering SC injection using the autoinjector. The usual sites for SC injection include the thigh, abdomen, and back of the upper arm.

Each daclizumab autoinjector is provided with the needle pre-attached. Autoinjectors contain a single dose only and should be discarded after use. Once removed from the refrigerator daclizumab should be allowed to warm to room temperature (about 30 minutes) prior to injection. External heat sources such as hot water must not be used to warm daclizumab. The daclizumab autoinjector must not be used if the liquid is cloudy or contains floating particles. The liquid must be colorless to slightly yellow.

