### **10.5.1. Elevated Liver Function Tests**

LFT procedures are described in Section 11.3.2. Prior to starting treatment with daclizumab, serum transaminases (ALT and AST) and bilirubin levels must be obtained. Serum transaminases must be monitored monthly during treatment and up to 4 months after the last study dose of daclizumab (see Section 4.2, for timing).

Study treatment must be temporarily suspended if a subject develops any of the following:

- ALT/SGPT, or AST/SGOT  $>3*ULN$ .
- ALT or AST have not exceeded 5 times the ULN; daclizumab may be resumed when ALT or AST have reached  $<2$  times the ULN.
- Any other clinically significant hepatic condition in the opinion of the Investigator including jaundice.

Note: For subjects who present with jaundice, an LFT must be performed as soon as possible. After a suspension, dosing of daclizumab may be resumed when ALT/SGPT and AST/SGOT are  $<2*ULN$  provided that the criteria for permanent discontinuation have not been met.

Study treatment must be permanently discontinued if a subject develops any of the following:

- Confirmed ALT or AST of  $>5$  times the ULN ALT/SGPT or AST/SGOT  $>3*ULN$  with concomitant elevation of total bilirubin  $>2*ULN$ .
- If a subject has treatment suspended for an LFT elevation and has also had a prior treatment suspension for an LFT elevation during daclizumab use, daclizumab must be permanently discontinued unless an alternative explanation for the LFT elevation unrelated to daclizumab use is clearly identified by the Investigator.

CONFIDENTIAL

The information contained herein may not be used, disclosed, or published without the written consent of Biogen MA Inc.

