### 11.3.2. Liver Function Test Assessments Prior to Daclizumab Dosing

Before a monthly dose of daclizumab is given, LFT results from prior testing performed within the previous 28 (+3) days must be reviewed by the Study Neurologist or their backup, and must be within protocol-required limits as described in Section 10.5.1.

LFTs can be performed as follows:

- Samples for LFTs must be drawn monthly and will be analyzed centrally for the purposes of this study. This includes any timepoints where there is not a scheduled

CONFIDENTIAL

The information contained herein may not be used, disclosed, or published without the written consent of  
Biogen MA Inc.

study visit and for samples which might be collected outside of the clinic (e.g., by visiting nurses). Accommodations will be made for LFT sampling and central testing for subjects choosing at-home dosing at Month 7, 8, 10 and 11.

- Results from either local or central LFT tests can be used for the medical management of the patient and to determine whether dosing should continue or be suspended at the monthly dosing timepoint (see Section 10).
- In any cases where LFTs are tested locally (e.g., at a local laboratory), samples must also be collected for central analysis for the purposes of this study.
- If the subject is administering daclizumab injections at home, site personnel must contact the subject after review of prior LFT results performed within 28 (+3) days to authorize the monthly injection, or if LFT results warrant, to instruct the subject to withhold their injection.
- LFTs following a treatment suspension must be performed through the central laboratory until the LFT abnormality has resolved. In cases where LFTs cannot be performed via central laboratory, repeat LFT results from local laboratory can be used for confirmation.

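### Protocol Section 10.5.1 gives two conflicting rules for restarting daclizumab after a liver-test suspension: one enzyme below 2x ULN, or both

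*Protocol*

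**What the plan says.** Protocol Section 10.5.1 has a list of suspension triggers, a Note, and a list of permanent-stop triggers. In each list, any single item is enough.

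- **Suspension list, first item:** ALT or AST above 3x ULN.
- **Suspension list, second item:** "ALT or AST have not exceeded 5 times the ULN; daclizumab may be resumed when ALT or AST have reached" less than 2x ULN. The connector is *or*.
- **Note:** "After a suspension, dosing of daclizumab may be resumed when ALT/SGPT and AST/SGOT are" below 2x ULN, "provided that the criteria for permanent discontinuation have not been met". The connector is *and*.
- **Permanent-stop list, first item:** a confirmed value above 5x ULN runs straight into a value above 3x ULN with total bilirubin above 2x ULN. The join reads "times the ULN ALT/SGPT or AST/SGOT", with no connector or punctuation.
- **Permanent-stop list, second item:** a second liver-test suspension is permanent unless the investigator clearly identifies another cause.

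Section 11.3.2 makes these limits operative. Liver results reviewed before each monthly dose "must be within protocol-required limits as described in Section 10.5.1". Section 4.2 and Table 1 footnote 10 state the bilirubin stop separately, at ALT or AST above 3x ULN: "since treatment must be permanently discontinued with the concomitant elevation of total bilirubin" above 2x ULN. Neither place asks for a confirmed value.

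**The concern.** Two sentences in one section govern the same decision and use different connectors. A neurologist clearing a monthly dose, or site staff authorising a home injection at Month 7, 8, 10 or 11, can reach opposite answers from the same results. What is at stake is a restart while one enzyme is still raised, or different practice across about 40 sites.

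The layout makes the section harder to apply. The second suspension item describes when dosing may resume, yet it is printed among the triggers. The first permanent-stop item looks like two criteria printed as one.

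**Working it through.** No sample size, alpha or power figure is involved, so the check is to apply the printed rules to test values. Values are multiples of ULN, and bilirubin is normal unless stated.

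**1. The restart rules.** The list item is met when min(ALT, AST) < 2. The Note is met when max(ALT, AST) < 2 and no permanent-stop criterion is met. With no stop criterion met, the two disagree whenever the lower enzyme is below 2 and the higher is at or above 2. The suspension trigger, max(ALT, AST) > 3, settles the cases above 3. The conflict that remains is: lower enzyme < 2 and 2 ≤ higher enzyme ≤ 3.

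| ALT, AST after a suspension | List item (*or*) | Note (*and*) | Above 3x trigger | Result |
|---|---|---|---|---|
| 1, 1 | restart | restart | not met | agree |
| 1.5, 2.5 | restart | no restart | not met | conflict |
| 1.5, 4 | restart | no restart | met | stays suspended |
| 4, 4 | no restart | no restart | met | stays suspended |

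**2. The 5x line as a trigger.** Taken literally as its own suspension item, it is met by ALT 1 and AST 1, so every subject with normal enzymes would be suspended. It makes sense only as a resume condition attached to the item above it.

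**3. The permanent-stop item.** There are three ways to parse it:

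- *Bilirubin qualifies both thresholds, as alternatives:* (>5 and bilirubin >2) or (>3 and bilirubin >2). This reduces to >3 and bilirubin >2, so the 5x clause does nothing.
- *All conditions required together:* >5 and >3 and bilirubin >2. ALT 4 with bilirubin 2.5 then gives no stop, which contradicts Section 4.2 and Table 1 footnote 10.
- *Two separate triggers:* confirmed >5; or >3 with bilirubin >2. ALT 4 with bilirubin 2.5 gives a stop, and so does a confirmed ALT of 6 with normal bilirubin. This agrees with Section 4.2 and gives the 5x clause a purpose.

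Only the third parsing fits the rest of the protocol.

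**4. What PDF reading can explain.** A lost line break could produce the run-on stop item, and lost indentation could turn the 5x line into a separate item. Neither can change *and* into *or*.

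**The case against.** The strongest reply is that the Note settles the matter. It is a complete sentence, it expressly covers the period after a suspension, and meeting both statements means meeting the stricter one. Exclusion criterion 10 points the same way, since either enzyme at 2x ULN or more bars entry. This makes the intended rule fairly clear, but it does not remove the conflict. The list item is also a permission to restart, and nothing ranks one above the other.

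A second reply is that the label governs. Section 10.1 says "Refer to and follow the prevailing local labeling", and Table 1 footnote 5 says "Abnormal AST/ALT values as described in the product label will lead to treatment suspension or discontinuation". The label may well resolve the point. It is not in the documents, footnote 5 concerns the safety follow-up, and Section 11.3.2 sends the site to Section 10.5.1, not to the label.

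A reader might also infer three stronger things, and the documents support none of them:

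- *That dosing may restart after a confirmed isolated value above 5x ULN.* The 5x line, read naturally as a resume condition (neither enzyme has exceeded 5x), already bars this. It also needs a parsing of the stop item that either empties the 5x clause or contradicts Section 4.2.
- *That the sponsor misprinted the two lists.* Both faults may come from text extraction.
- *That the 6% of daclizumab subjects with elevations above 5x ULN in the active-controlled trial (Section 5.1.4) sizes the problem.* That figure counts elevations, not wrong restarts, and says nothing about one enzyme lingering between 2x and 3x ULN.

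**Conclusion.** The conflict between the two restart rules is real and is in the wording itself. It bites in a narrow band: after a suspension, one enzyme is below 2x ULN and the other lies from 2x to 3x ULN. Outside that band the two rules agree, or the 3x trigger or the permanent-stop list decides.

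The separate 5x item and the run-on stop item are secondary. Their meaning can be recovered from the resume condition, Section 4.2 and Table 1 footnote 10.

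Severity is minor. No endpoint, sample size or analysis uses the restart rule; for liver tests the SAP only lists and grades values and summarises ALT or AST at 3x ULN or more by concurrent bilirubin. The number of subjects who might be dosed wrongly cannot be estimated, because the documents give no rate for the enzyme pattern concerned. SAP Section 2 records that the study has been terminated. The conclusion assumes that the extracted connectors are the printed ones and that both sentences govern the same restart decision.

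**What to change.** Reword Section 10.5.1 as follows:

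1. Keep the suspension trigger as ALT or AST above 3x ULN, with no upper limit. A single unconfirmed value above 5x then suspends dosing without a further rule.
2. Delete the *or* restart wording and state one rule: dosing resumes only when ALT and AST are both below 2x ULN and no permanent-stop criterion is met. The 5x limit is then carried by the permanent-stop list.
3. Print two separate permanent-stop items: confirmed ALT or AST above 5x ULN; and ALT or AST above 3x ULN with total bilirubin above 2x ULN, the latter without confirmation, as in Section 4.2 and Table 1 footnote 10.

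The cost is a few lines in one section, with no new procedure, visit or subject. As the study has stopped, the correction serves the written record and any later protocol that reuses this rule.

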## 11. DATA COLLECTION

A written, signed Informed Consent Form (ICF) and all authorizations required by local law (e.g., PHI in North America) must be obtained prior to performing any tests or assessments under this protocol.

### 11.1. Site Personnel

For each subject, the Principal Investigator will designate the following study site personnel:

- A primary Study Neurologist and backup neurologist.
- A primary and backup Nurse (or Study Coordinator).
- A primary and backup Examining Technician.
- An MRI Technician.
- A Pharmacist (or authorized designee).

The Study Neurologists may designate another neurologist at the center who meets the same qualifications to perform the [REDACTED] assessments and other neurologic assessment during the trial.

The primary Study Neurologist will be responsible for the following:

- Management of the routine neurological care of the subject.
- Assessment (including assignment of causality) and treatment of AEs and MS relapses.
- Obtaining an [REDACTED] score.
- Review of selected hematology and all blood chemistry results from the central laboratory.
- Assessment of LFT results, as detailed in Section 11.3.2.
- Monitoring and follow-up of any abnormal hepatic tests.

Hematology and blood chemistry data will be sent to the investigational sites to aid in management of the subject.

The primary Nurse or Study Coordinator will be responsible for the following:

- Assisting the Study Neurologist in subject management, including the treatment of AEs, the treatment and assessment of disease relapses, and the recording of AEs and concomitant medications.
- Monitoring the [REDACTED] scores.
- Collection of blood samples and obtaining vital signs.
- Study treatment administration/dispensation/accountability.

The MRI Technician will be responsible for the following:

CONFIDENTIAL

The information contained herein may not be used, disclosed, or published without the written consent of Biogen MA Inc.

- Performing a brain MRI scan with and without Gd at all protocol-required timepoints. Study-specific MRI scan procedures and protocols, which will be provided prior to study start, must be followed.

The Pharmacist (or authorized designee) will be responsible for the following:

- Storage, distribution, and accountability of study treatment.

## **11.2. Assessments**

### **11.2.1. Assessments at Screening**

The following variables will be collected during screening at the enrollment visit:

- Date of signed ICF.
- Confirmation of eligibility criteria.
- Demographic information: age at screening (years), sex.
- MS disease history (type of MS, date of initial MS diagnosis, relapse history).
- Relevant medical history and co-morbidities including: assessment of clinically significant medical and surgical history and concomitant diseases, and known cardiovascular risk factors. Of interest are: smoking; alcohol consumption; subject and family history of high cholesterol; high blood pressure; cardiac disease; peripheral artery disease; arrhythmia; cerebrovascular disease; diabetes mellitus; HIV; hepatitis C virus (test for HCV Ab) or hepatitis B virus (test for HBsAg and/or HBcAb); history of transplantation or any anti-rejection therapy.
- Prior use and duration of natalizumab (e.g., start and stop dates, initial dose, dose reductions or escalations, dosing frequency).
- Prior use and duration of other therapies for MS (if any) (e.g., start and stop dates, initial dose, dose reductions or escalations, prescribed dosing frequency, reason for discontinuation, prior use of immunosuppressants).
- Vital signs.
- Physical examination.

Refer to Section 4 for the timing of assessments.

### **11.2.2. Assessments at Baseline and Follow-up**

#### **11.2.2.1. MS Treatments and Concomitant Medications**

MS treatments and concomitant medications will be recorded as follows:

- Daclizumab dose and dates of administration on-site.
- Daclizumab self-administered dose, and dates of administration recorded by subject in dosing diary (beginning at Month 7, where applicable).

CONFIDENTIAL

The information contained herein may not be used, disclosed, or published without the written consent of Biogen MA Inc.

- Current use (i.e., at screening) of immunomodulatory, immunosuppressive (including corticosteroids), anti-neoplastic agents, and other approved MS therapies (if any).
- Current use (i.e., at screening) of non-MS therapy medications (if any).

Refer to Section 4 for the timing of assessments.

#### 11.2.2.2. Laboratory Assessments

As per Section 11.3.2, a central laboratory will perform laboratory analyses and provide reference ranges for each test.

Laboratory assessments will include the following:

- CBC including hemoglobin, hematocrit, platelet count, red blood cell count and white blood cell count (with differential).
- Blood chemistry including sodium, potassium, chloride, total bilirubin, alkaline phosphatase, lactate dehydrogenase, gamma glutamyl transferase, blood urea nitrogen, creatinine, and bicarbonate and bilirubin.
- [REDACTED]
- [REDACTED]
- [REDACTED]
- [REDACTED]
- LFT including ALT/SGPT, AST/SGOT, and bilirubin:
  - LFT is to be conducted monthly in a blood draw conducted.
  - LFT will be performed only if the subject is continuing daclizumab or if less than 4 months have passed since the subject discontinued treatment and monitoring is deemed appropriate by the Investigator.

Refer to Section 4 for the timing of assessments.

#### 11.2.2.2.1. [REDACTED]

[REDACTED]

[REDACTED]

CONFIDENTIAL

The information contained herein may not be used, disclosed, or published without the written consent of Biogen MA Inc.

### 11.2.2.3. Safety

Safety assessments will include the following:

- SAEs.
- AEs, including laboratory abnormalities.
- Vital Signs.
- Physical Assessment (i.e., normal or abnormal).

An additional safety follow-up visit at 4 months after the last study injection will be conducted remotely to evaluate potential delayed safety outcomes.

Refer to Section 4 for the timing of assessments.

### 11.2.2.4. Efficacy

Efficacy assessments will include the following:

- MS relapse information including date of onset, date of visit, neurologic examination, duration, new and/or recurrent neurologic symptoms, hospitalization, and treatments including steroids. For the purposes of this study relapse is defined as new or recurrent neurologic symptoms not associated with fever, lasting at least 24 hours. New or recurrent neurologic symptoms that evolve gradually over months are to be considered disease progression, not an acute relapse. New or recurrent neurological symptoms that occur fewer than 30 days following the onset of a relapse as defined above are to be considered part of the same relapse.
- [REDACTED]
- Brain MRI scan including number and volume of Gd+ lesions, T1 hypointense lesions, and T2 hyperintense lesions.

Refer to Section 4 for the timing of assessments.

